Measuring the metabolic cost of fever: Indirect calorimetry in children with fever on the intensive care unit.

Protocol Version 2 (07.08.2016)

STUDY INVESTIGATORS:

Principal Investigator: [name]
PhD Student,
Respiratory, Critical Care and Anaesthesia Section,
UCL Great Ormond Street Institute of Child Health, London, UK
[contact]

Chief Investigator: [name] [name]
[name] Care Medicine
Respiratory, Critical Care and Anaesthesia Section,
UCL Great Ormond Street Institute of Child Health, London UK
[contact]

INTRODUCTION

Fever is a common immune response in children with infection or inflammation. While fever may potentiate the immune system to fight the pathogenic stimulus, energy is required to generate the raised temperature. This may be scarce in critical illness, particularly in children. We do not know how much energy is used in generating fever by children in the intensive care unit. This study aims to measure energy expenditure in children during and before/after they have a fever. We aim to do this using indirect calorimetry in at least 15 children, who are invasively ventilated on the intensive care unit. We will then calculate the average increase in energy expenditure required per 1°C rise in temperature in this population. If fever does not require a significant increase in energy expenditure in children on the intensive care unit, then treatment of fever may not have any benefits. If fever does require an increase in energy expenditure, this may counter the immunological benefits that fever confers. In such a case a randomised controlled trial comparing treatment and non-treatment of fever would be required.

BACKGROUND

Fever is an innate immune response to danger. Stimuli such as pathogens or tissue damage lead to a cascade of cytokine signals, including the release of pro-inflammatory cytokines such as TNF- α , IL-6 and IL-1. Many of these pro-inflammatory cytokines act upon the thermoregulatory centre of the hypothalamus via the release of prostaglandins, to increase the body's temperature set-point. The body responds by both reducing heat loss and increasing heat production to raise the body temperature^{1,2}.

The conservation of the fever response through billions of years of evolution (plants, insect, reptiles and mammals all increase their temperature in response to infection³⁻¹¹) suggest that fever has a beneficial effect. Animal studies show the following immunological benefits of fever range hyperthermia: (i) increased neutrophil release from the bone marrow, (ii) increased neutrophil tissue infiltration, for example in lungs tissue, (iii) increased cytotoxic activity of innate immune cells such as neutrophils and NK cells, (iv) increased phagocytic activity, (v) increased antigen presentation by dendritic cells, (vi) increased cytokine production and release².

This correlates with some clinical outcome studies. Malaria induced fever was successfully used to treat neurosyphilis in the pre-antibiotic era¹². Anti-pyretic treatment increases the duration of virus shedding and illness in varicella and rhinovirus infection¹⁴⁻¹⁵. Population level influenza rates may increase with regular anti-pyretic treatment¹⁶. In critically-ill patients, especially those with infection, a maximum temperature at intensive care unit admission of 38.5-39.5°C was associated with the lowest risk of mortality¹⁷⁻¹⁸. However randomised controlled trials treating fever with anti-pyretics or placebo in critical illness have not demonstrated any risks of treating fever¹⁹⁻²³.

Balancing the immunological benefits of fever are several potential detrimental effects. Hyperthermia can cause protein degeneration, leading to direct cell damage and death. This can lead to loss of gastrointestinal tract integrity, decrease in glomerular filtration rate, liver dysfunction, myocardial damage and arrhythmias, brain injury and lowering of the seizure threshold²⁴. Most of these deleterious effects occur in sterile forms of pyrexia, especially at high grade temperatures. However in critical illness the generation of fever itself may be deleterious. Energy is required to produce heat: in fever, this can be through uncoupling of the electron transport chain leading to heat dissipation in brown fat, or through shivering²⁴. As critical illness is characterised by an

imbalance of energy delivery and consumption, the energy requirements to generate a fever may be unaffordable²⁵.

The energy requirements of fever have previously been measured in adult patients on the intensive care unit. Manthous et al studied 12 febrile patients on the intensive care unit during cooling after sedation and paralysis. For each 1°C drop in temperature, the reduction of energy expenditure was 10% of the baseline. This was also accompanied with a reduction in cardiac output, and no change in oxygen extraction (the ratio between oxygen consumption and delivery)²⁶. Similar associations between temperature reduction and decrease in energy expenditure with cooling have been demonstrated in the context of brain injury²⁷⁻²⁸.

In children, energy expenditure has been shown not to be raised in febrile infants admitted to hospital. In a cohort of 12 children, although 8 had an increase in energy expenditure when febrile, overall there was no difference²⁹. However this was conducted in children who were not critically unwell or in intensive care. It is possible that these children were able to increase their temperature by preventing heat loss. Children in intensive care may not have the ability to do so, due to disease related factors such as shock and vasoplegia, or treatment related factors, such as exogenous vasodilators. Children admitted to hospital with over 40% burns had an increase in energy expenditure with fever by up to 30% of baseline³⁰. These children were likely to have more unregulated surface heat loss due to skin barrier compromise, but equally were likely to be hypermetabolic following their initial injury. In an analysis of cytokine levels and metabolic rate in critically-ill children, Briassoulis et al found that the predominant metabolic pattern in acute critical illness in children was that of hypometabolism, during which energy expenditure did not correlate with levels of IL-6 and IL-10, both fever-inducing cytokines³¹.

Therefore we still do not know if energy expenditure is increased in children with febrile illness in the intensive care unit. Given the immune benefits of fever, there may be an argument to not treat fever in critically ill children as any advantage in host response may be beneficial. However, if the energy expenditure associated with fever is high, treatment of fever may have a benefit.

AIM OF STUDY

To understand the changes, if any, in the energy expenditure of critically-ill children with fever

STUDY OBJECTIVES

To measure the energy expenditure using indirect calorimetry in mechanically ventilated children admitted to the intensive care unit before, during and after fever.

HYPOTHESIS

Null hypothesis: Fever will be associated with <10% difference of baseline energy expenditure per 1°C change in temperature in critically-ill children ventilated on the intensive care unit

Alternative hypothesis: Fever will be associated with a >10% difference of baseline energy expenditure per 1°C change in temperature

STUDY DESIGN

Prospective observational cohort study

STUDY POPULATION

Children admitted to the paediatric intensive care unit at Great Ormond Street Hospital with suspected infection, following trauma or major surgery, who are likely to develop a fever.

ELIGIBILITY CRITERIA

Inclusion criteria:

- Children >10kg (The MedGraphic Ultima CCM calorimeter has been used safely in children as low as 10kg)
- Children with suspected infection, following trauma, or post-major surgery

Exclusion criteria:

- Children post brain injury
- Children with refractory status epilepticus
- Children post cardiac arrest
- Children post cardiac bypass
- Children with cardiac arrhythmias
- Children not invasively ventilated
- Children with a greater than 5% leak around their endotracheal tube
- Children with a fraction of inspired oxygen (FiO_2)>0.60
- Children above 16 years of age

STUDY OUTCOMES

Primary outcome: Change in energy expenditure per degree Centigrade change in temperature

Secondary outcome: Change in oxygen extraction ratio (ratio of oxygen consumption to oxygen delivery) per degree Centigrade change in temperature using oxygen delivery data from the Lidco Rapid (LIDCO Ltd, UK) cardiac output monitor if in place.

STUDY PROCEDURES

Screening and Recruitment

- All patients will be screened each morning (Mon-Fri) by the PI for weight, ventilation status and likelihood of developing a fever (The PI is part of the wider clinical team)
- The PI will ask the clinical team on call if calorimetry is suitable for the identified patient/s
- If the clinical team feel this is appropriate, the PI will ask consent of the parents to undertake indirect calorimetry

Study procedure

1. Once consented, calorimetric measurement will be undertaken using the MedGraphic Ultima CCX, Minnesota, USA). This will be done in the following steps:
 - a. Assess the patient for stability:
 - i. no change in inotropes (dopamine, adrenaline, noradrenaline, vasopressin, milrinone, dobutamine) in previous hour
 - ii. no change in ventilator settings including FiO₂ in the previous hour
 - iii. FiO₂ <0.6
 - iv. tidal volume ventilation >60ml (ideally greater than 100ml)
 - v. air leak around endotracheal tube (ETT)<5%
 - vi. no increases in sedation in past hour
 - vii. no major stimulatory events (physiotherapy, turning, suction) in the previous hour
 - b. Record demographic data, ventilator settings and measurements, calorie intake, heart rate, blood pressure, cardiac index (if monitored), drug infusion rates, use of paralysis, COMFORT or sedation score, temperature
 - c. If the patient is stable, then start measurement of energy expenditure (calibrate prior to measurement, attach gas sampler to end of ETT to ventilator end of capnograph/flow sensor).
 - d. Stop measurement immediately if any deterioration in ventilation with measurement
 - e. After 30 minutes (or sooner if steady state is reached i.e. 5 consecutive minutes of less than 10% variation in O₂ and CO₂ concentrations) stop measurement
2. If patient develops temperature >38°C (axillary or central measurement) within the next 4 hours (or longer only if all variables are the same as baseline), repeat step 4 a-c prior to anti-pyretic administration (with half hourly data collection). The calorimeter will be left on the patient for continuous data collection until the temperature falls below 38°C.
3. If continuous measurement is not possible because of clinical needs (nursing or medical request, need for suctioning, patient instability), a 3rd measurement will be taken when the temperature is below 38°C

If the patient is febrile at screening, measurement will start at step 2

Patient safety

The calorimeter fits in to the ventilator circuit. This requires very brief disconnection of the circuit to attach the sampling connector. Disconnection of this nature is routine practice in the intensive care unit (for example during suctioning) and is well tolerated.

The calorimeter samples air from the ventilator circuit at a constant rate of 100ml/min. This may affect ventilation in small children. The Medgraphic Ultima CCM is licensed for use for patients with tidal volumes of 100ml or more. This will usually equate to children around 15kg. However our collaborators in Addenbrooke's Hospital, Cambridge (Dr [name]) have used the Medgraphic Ultima CCM safely in children down to 10kg.

During measurement we will monitor the child's respiratory rate, oxygen saturation levels and end tidal CO₂. If any of these values change significantly, as judged by the bedside nurse or the PI, calorimetry will be discontinued.

Data collection

Data will be collected for

- Demographic data (ID, weight, height, age, sex, diagnosis)
- Inspired and expired O₂ and CO₂; VO₂ and VCO₂; Respiratory Quotient; Energy expenditure (as measured and displayed by the MedGraphics Ultima CCM calorimeter)
- Physiological variables (heart rate, blood pressure)
- IF CARDIAC OUTPUT MONITOR IN PLACE: stroke volume and cardiac index (as measured by Lidco Rapid, LIDCO Ltd, UK) and latest haemoglobin
- Inotrope infusion doses
- COMFORT or sedation score as recorded
- Paralysis (yes/no)
- Temperature
- Nutritional intake in last 24 hours or since admission

Data apart from demographic data will be collected at the start of each recording and hourly if continuous recording

If cardiac monitoring is in place, continuous data (as recorded by the Lidco Rapid) will be used to calculate oxygen delivery.

STATISTICAL ANALYSIS

Sample size: Not enough data exists to ascertain the standard deviation of energy expenditure using the Medgraphics Ultima CCM calorimeter in critically ill children over the time period to be measured. However a standard deviation of 10% has been observed in critically ill children by groups who have measured energy expenditure in large numbers of children (personal communication from Dr [name], Imperial College, London). Based on this, for a 10% effect size, with a one-tailed α of 0.05 and (1- β) of 0.8, a sample size of 10 children would be needed, provided a 1°C of temperature is seen. An analysis of temperature change following over 5000 doses of paracetamol in febrile children suggested a mean reduction of temperature by 0.7°C. Based on this therefore we will need $10 \times 1/0.7 = 15$ patients

However it is likely that our sample will have several confounders which will need to be taken into account by multi-variable analysis. Therefore we will aim to recruit at least 15 children with measurements with and without fever (ideally before-during and after fever), but will try and recruit as many children as possible over the 12 month study period. Approximately 300 patients admitted to PICU at Great Ormond Street Hospital per year are above 10kg. Of these, approximately 75-100 patients are electively admitted, 30 post-major surgery (mostly spinal surgery). 30% of children post spinal surgery develop a fever in the first 24 hours. In addition the remaining 200 children are admitted as an emergency. 80% of children admitted as an emergency are treated for a suspected infection, the remainder post trauma. Again 30-50% of children admitted with an infection or trauma develop a fever within the first 24 hours. Therefore each year approximately 75-80 patients will be >10kg, ventilated, and will develop a fever within the first 24 hours of admission, with a proportion developing fever later on in admission (e.g. from nosocomial infections).

Statistical analysis: Uni-variable analysis using paired t-tests will be undertaken by comparing the energy expenditure with and without fever, divided by the change in temperature. Multi-variable analysis using a multi-level regression model will be used using

- Change in energy expenditure as the outcome variable
- Patient ID as the random effect variable
- Change in temperature, COMFORT score, vasoactive inotrope score, heart rate, blood pressure, and paralysis as a binary variable as fixed effect variables

If cardiac output monitoring is in place, then the oxygen extraction can be calculated as VO_2/DO_2 , where,

$DO_2 = \{cardiac\ index \times ((oxygen\ saturation\ of\ haemoglobin \times haemoglobin\ concentration) + 0.0031 \times partial\ pressure\ of\ oxygen)\}$

and VO_2 is measured from the calorimeter

ETHICAL CONSIDERATIONS

The study will be conducted in accordance to Good Clinical Practice principles and the principles of the Declaration of Helsinki.

Informed consent will be sought from parents/guardians with parental responsibility prior to measurement. Consent forms will be stored in the Great Ormond Street Critical Care Research Office securely.

Data will be stored and processed electronically in a secure password protected NHS IT network according the principles of the institutional information governance policy. Patient identifiable data will be minimised to unique patient hospital number. The storage of data will be consented for.

Baseline energy expenditure data may be shared with collaborators anonymously to further the understanding of metabolic activity in critically ill children. Consent for this will explicitly sought.

OUTCOMES AND SIGNIFICANCE

If the null hypothesis is true, then the treatment of fever in critically-ill children can be questioned, especially given the immunological benefits. If the alternative hypothesis is true, then the overall risk- benefit balance of treating or not treating fever in critically ill children will have to be assessed in the form of a randomised controlled clinical trial.

Research findings will be disseminated in national and international intensive care conferences, and peer-reviewed medical/scientific journals

REFERENCES

4. Kluger MJ. Fever in the frog *Hyla cinerea*. *J Therm Biol.* 1977;2:79-81
7. Stitt JT. Prostaglandin E1 fever induced in rabbits. *J Physiol.* 1973 Jul;232(1):163-79

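### The hypotheses are split at 10% per 1°C, but the sample size and paired t-test work against zero, so under the planning inputs a true null can be rejected about 82% of the time

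*Combined protocol and SAP*

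**What the plan says.** The Hypothesis section puts the boundary at 10% of baseline energy expenditure per degree. The null is "Fever will be associated with <10% difference of baseline energy expenditure per 1°C change in temperature", set against "Alternative hypothesis: Fever will be associated with a >10% difference of baseline energy expenditure per 1°C change in temperature". The Study Outcomes section defines the quantity of interest: "Primary outcome: Change in energy expenditure per degree Centigrade change in temperature".

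Under Statistical Analysis, the sample size paragraph assumes an SD of 10% and is set "for a 10% effect size, with a one-tailed α of 0.05" with 80% power. It arrives at 10 children if the temperature changes by 1°C, then scales by 1/0.7 to 15. The analysis paragraph states: "Uni-variable analysis using paired t-tests will be undertaken by comparing the energy expenditure with and without fever, divided by the change in temperature". It adds a multi-level regression with temperature change among the fixed effects. Neither analysis is given a test value of 10%, a margin, or a confidence-interval rule.

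Outcomes and Significance then draws one conclusion from each hypothesis. The first begins "If the null hypothesis is true, then the treatment of fever in critically-ill children can be questioned"; the second, should the alternative be true, is that a randomised trial is needed. The Introduction frames the same choice differently: "If fever does not require a significant increase in energy expenditure in children on the intensive care unit", which reads as a comparison with zero.

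**The concern.** The effect the study is powered to detect is the boundary of its own null hypothesis. If the test value were 10% per °C, a true cost of 10% per °C would lie at zero distance from the null, and no sample size could give 80% power. If the test value is zero, as a paired t-test implies unless told otherwise, the test does not address the stated hypotheses.

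Both directions of inference fail. A significant result against zero does not show a cost above 10%. A non-significant result does not show a cost below 10%, so it cannot establish that the stated null is true. The two conclusions in Outcomes and Significance are attached to hypotheses that differ only in the side of 10% on which the cost falls.

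The Background cites an adult study with a 10% change per 1°C. The protocol's own evidence therefore points to values near the boundary, where a test against zero most often rejects a null that is true as stated.

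**Working it through.** **Inputs from the protocol.** SD 10%, effect 10%, one-tailed alpha 0.05, power 0.80, mean temperature change 0.7°C, minimum n = 15 (Statistical Analysis); hypothesis boundary 10% per 1°C (Hypothesis).

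**Assumptions.** The 10% is the SD of the within-child change (the protocol does not say whether it is this or the SD of a single measurement), and every child changes by exactly 0.7°C.

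**Method.** One-sample t-test on the within-child change, with power from the noncentral t distribution on n − 1 degrees of freedom. For a true cost β and test value β₀, both in % per °C, the noncentrality is (β − β₀) × 0.7/10 × √n.

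**1. The plan's own figure.**
- At 1°C the standardised effect against zero is 10/10 = 1. Exact t gives n = 8 one-sided (power 0.815) and n = 10 two-sided (power 0.803). The stated 10 equals the two-sided result and is close to the one-sided one.
- 10/0.7 = 14.3, rounded up to 15.
- Directly, at 0.7°C with n = 15 and β₀ = 0, the noncentrality is 0.7 × √15 = 2.711 and one-sided power is 0.824.

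The plan's size therefore reproduces with a null of zero.

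**2. The same design with the stated boundary.** With β₀ = 10 and β = 10 the noncentrality is 0, so power is 0.05 at any n.

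**3. Rejection of zero while the stated null is true (n = 15, 0.7°C, one-tailed 0.05).**

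| True cost, % per °C | Noncentrality | P(significant) |
|---|---|---|
| 0 | 0 | 0.050 |
| 3 | 0.813 | 0.192 |
| 5 | 1.356 | 0.361 |
| 8 | 2.169 | 0.662 |
| 9 | 2.440 | 0.750 |
| 9.9 | 2.684 | 0.818 |
| limit at 10 | 2.711 | 0.824 |

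**4. Precision.** The SD per °C is 10/0.7 = 14.29, and the standard error is 14.29/√15 = 3.69. With t(0.95, 14) = 1.761, the 90% interval has half-width 1.761 × 3.69 = 6.50. At this SD:
- an observed mean above about 6.5% per °C is significant against zero, so an estimate of 7% would be significant while lying inside the stated null;
- the upper limit falls below 10% only if the estimate is below 10 − 6.5 = 3.5% per °C;
- the lower limit exceeds 10% only if the estimate is above 10 + 6.5 = 16.5% per °C.

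**5. Power of a test against 10% (n = 15).** Power is 13% at a true 12% per °C, 36% at 15% and 82% at 20%; 80% is reached at about 19.6%. For 80% power at 0.7°C, the required n is 317 at a true 12%, 142 at 13%, 52 at 15% and 15 at 20%. The documents posit no cost above 10% per °C for this population, so these values are an illustrative range.

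**6. Sensitivity of the 82% limit.**
- 1°C change: 97.9% (n = 15) or 89.8% (n = 10).
- n = 30 at 0.7°C: 98.2%.
- Two-sided 0.05: 71%.
- 10% as the SD of a single measurement with zero within-child correlation (SD of change 10 × √2 = 14.1%): 57%.
- An assumed between-child SD of temperature change of 0.2 to 0.3°C, by simulation: 72% to 62%.

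**The case against.** The protocol never says that it tests against zero. Dividing each child's difference by the temperature change gives a per-child slope, which can be compared with 10 as easily as with 0. The 10% effect could even be read as an excess over the boundary: a true 20% per °C tested against 10% gives the same noncentrality and the same 82.4% power. It is right that the test value is inferred. But the excess reading appears nowhere, the cited adult figure is 10% rather than 20% per 1°C, and a paired t-test with no stated value compares with zero. If a test against 10% was intended, the plan still has to say so and justify a planning value of 20%.

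The 82% is also not a ceiling. It depends on the planning inputs and moves in both directions, as the sensitivity results show; the protocol also hopes to recruit more than 15 children. That stands, and the figure should be quoted with its conditions. Every variant nevertheless remains far above 5%.

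A further argument is that zero is the real null, since the Introduction and the stated aim ask whether there is any change, and the Hypothesis wording is the outlier. That may be so, but it confirms that the document holds two different nulls. The primary outcome as a per-degree estimate and the multi-level model do not resolve this, because neither carries a 10% comparison.

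Finally, this is a single-centre observational study with cautiously worded conclusions, and the remedy is a matter of wording. That bears on cost, not on whether the stated conclusions follow from the planned test.

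**Conclusion.** The concern holds. The hypotheses, sample size, test and conclusions do not address one question. The stated size is coherent only against zero, whereas the hypotheses and the conclusions drawn from them concern 10% per °C.

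Under the planning inputs, the probability of a significant result while the stated null is true rises from 5% at no cost to about 82% just below the boundary. Under the alternative assumptions examined, the limit at the boundary runs from 57% to 98%. The mismatch itself depends on none of these figures. It rests on the absence of any 10% test value or interval rule, and on the ordinary reading of a paired t-test. This should be corrected before analysis, because it determines what the study may conclude.

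**What to change.** Choose one null and carry it through the document.

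**If 10% per °C is the intended threshold**
- Express the cost as a percentage of afebrile energy expenditure per °C and report the mean with a two-sided 90% confidence interval, equivalent to two one-sided 5% tests.
- Conclude that the cost exceeds 10% only if the lower limit is above 10, and that it is below 10% only if the upper limit is below 10. Otherwise call the result inconclusive.
- State how the temperature coefficient in the multi-level model will be compared with the same threshold.
- Describe the existing 80% power as power to detect a non-zero change, and give the expected half-width (about 6.5% per °C at n = 15 under the planning inputs), saying which SD the 10% represents.

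**If zero is the intended null**
- Rewrite the hypotheses as no increase versus an increase.
- In Outcomes and Significance, replace the conclusion that depends on the null being true with one based on the confidence interval.

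Either route changes wording in the Hypothesis, Statistical Analysis, and Outcomes and Significance sections. No extra patients or measurements are required. The price is candour: with 15 children, a claim about the 10% threshold is much less well powered than the present text suggests, and an inconclusive result is a realistic outcome.

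### The stability check before each reading screens out recent increases in sedation but not decreases, so the effect of lighter sedation can enter the fever comparison

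*Combined protocol and SAP*

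**What the plan says.** All references are to the combined protocol and SAP.

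- **Study procedure, step 1a.** Item (i) requires "no change in inotropes (dopamine, adrenaline, noradrenaline, vasopressin, milrinone, dobutamine) in previous hour" and item (ii) "no change in ventilator settings including FiO₂ in the previous hour". Item (vi) requires "no increases in sedation in past hour". Item (vii) requires "no major stimulatory events (physiotherapy, turning, suction) in the previous hour".
- **Step 1b** records, among other things, "drug infusion rates, use of paralysis, COMFORT or sedation score, temperature".
- **Step 1e** ends a reading "After 30 minutes (or sooner if steady state is reached i.e. 5 consecutive minutes of less than 10% variation" in gas concentrations.
- **Step 2** takes the fever reading if the temperature rises above 38°C "within the next 4 hours (or longer only if all variables are the same as baseline", before any anti-pyretic is given. It repeats the assessment, citing a step 4 that does not exist; I read this as step 1a-c. Recording then continues until the temperature is below 38°C.
- **Step 3** provides a separate reading below 38°C when continuous recording is not possible. It does not restate the stability check.
- **Study outcomes.** The primary outcome is "Change in energy expenditure per degree Centigrade change in temperature".
- **Statistical analysis.** The uni-variable step is a paired t-test of EE with and without fever, scaled by the temperature change. The multi-level model has COMFORT score among its fixed effects, but no sedative dose and no change in sedation.

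**The concern.** The stability check exists so that the two readings of a pair differ in temperature and as little else as possible. For sedation it guards one side only. A recent increase, which might lower EE, disqualifies a reading; a recent decrease, which might raise EE through arousal, does not. No reason is given for the difference from items (i) and (ii).

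Sedation is often reduced as a stay goes on, so a decrease may fall more often on the later reading of a pair than at random. If the later reading is the febrile one, the slope is inflated. If it is the afebrile one, the fever effect is masked. Children who are febrile at screening start at step 2, so they supply only fever-to-after pairs and are exposed to masking. Because the outcome is expressed per degree, any error in EE is divided by a temperature change that the plan expects to be below 1°C, which enlarges it.

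**Working it through.** **1. Does anything else screen a decrease?**
- Item (vii) names physiotherapy, turning and suction. Lightening of sedation is not among them.
- The same-as-baseline condition in step 2 applies only beyond 4 hours, and covers sedation only if sedation counts as one of the variables.
- The steady-state rule does not exclude such a reading. A reading may end at 30 minutes without steady state, and stable gas values can still sit at a higher level.
- The check is not restated for the step 3 reading, or for the afebrile end of a continuous recording.
- The paired t-test has no sedation term.

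So a decrease in the past hour passes, at least within the 4-hour window and for the afebrile reading after fever.

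**2. The plan's own figure.** The sample size is 10 × 1/0.7 = 14.3, rounded up to 15. The 10 rests on an effect of 10% and an SD of 10%, a standardised effect of 1. A paired t-test at 0.05 with 80% power needs 8 children one-tailed and 10 two-tailed, so the stated 10 is close to the first and equal to the second. The sedation wording does not alter this. Only n = 15, the SD of 10% and the 0.7°C change are carried forward.

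**3. Shift for one child.** Let x be the percentage rise in EE in one reading due to lighter sedation. The documents give no value; I assume 3-10%. The child's slope moves by x / 0.7:
- 3 / 0.7 = 4.3% per °C
- 10 / 0.7 = 14.3% per °C

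**4. Shift in the mean.** Let f be the share of children affected, assumed to be 0.25. If all shifts go the same way, the mean moves by f × x / 0.7:
- 0.25 × 4.3 = 1.1% per °C
- 0.25 × 14.3 = 3.6% per °C

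**5. Mixed pair types.** Let p be the share of affected pairs that are before-to-fever, the rest being fever-to-after, with the decrease always before the later reading and the same x in both. The net shift is f × x × (2p − 1) / 0.7. At p = 1 this gives the values in step 4. At p = 0.75 it is half of them, about 0.5 to 1.8% per °C. At p = 0.5 the mean shift is zero and what remains is added noise.

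**6. Scale.** Taking the plan's 10% as the SD of the within-child difference, the standard error of the mean slope at n = 15 is 10 / 0.7 / √15 = 3.7% per °C. The top of the one-direction range is about one standard error, and roughly a third of the 10% per °C threshold in the Hypothesis section (3.6 / 10 = 0.36).

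**The case against.** **The size is assumed.** Neither the EE effect of lighter sedation nor the frequency of decreases is in the documents. This stands, and the range shows only what the assumptions imply.

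**The biases oppose each other.** The plan seeks readings before, during and after fever, so inflation and masking partly offset. This also stands, and makes the one-direction range an upper case.

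**The plan already adjusts.** It says that confounders need multi-variable analysis, includes COMFORT score, and records infusion rates from which affected readings could be found. This stands in part. The Data collection section takes COMFORT or another sedation score as recorded, so COMFORT may be missing for some children. The model does not say whether level or change enters, and it has six fixed effects against a minimum target of 15 children. Data collection lists infusion doses for inotropes only, and no rule uses sedative rates to flag or exclude a reading.

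**A past-hour rule misses earlier weaning.** A child whose sedation was reduced 90 minutes before the fever reading would pass a two-way check and might still have a higher EE. This stands; rewording closes only part of the gap.

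**Stronger readings.** A reader might infer that the wording is likely to produce a false positive result. With a quarter of fever readings raised by 10%, n = 15, SD 10% and no true effect, a one-tailed 0.05 test would reject zero difference about 24% of the time. That test is against zero, not against the protocol's 10% hypothesis, and it again puts every shift in one direction. A reader might also infer that sedation is not adjusted for at all, which the COMFORT term contradicts. The documents support neither reading.

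**Conclusion.** The asymmetry in step 1a is real, and no other rule closes it within the 4-hour window or for the afebrile reading after fever. It leaves the paired comparison open to a bias whose direction depends on the pair type. Under the stated assumptions (3-10% rise in EE, a quarter of children, one direction, 0.7°C) the mean slope moves by at most 1.1-3.6% per °C, and by less with mixed pairs. The documents show neither that a shift of this size will occur nor that it would overturn the conclusion. This is a minor point, held with low confidence as to size, and worth acting on mainly because the remedy is cheap.

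**What to change.** 1. Reconcile item (vi) with items (i) and (ii), so that the measurement check excludes a change in sedation in either direction in the past hour.
2. Apply the check to every analysed reading, including the step 3 reading and the values taken from continuous recording.
3. Where waiting would lose the fever reading that must precede the anti-pyretic, take the reading, flag it, and repeat the paired analysis without flagged readings.
4. With each reading, record sedative infusion rates and any sedation change in the past hour. Report within-pair differences in sedation, since the past-hour rule does not remove differences due to earlier weaning.

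The cost is a wording change and two or three extra recorded items. Some readings will wait up to an hour or carry a flag, and the sensitivity analysis will have slightly fewer pairs. A strict rule without the fallback in item 3 could lose whole pairs from a target of only 15. The change governs which readings count, not how a child is sedated.
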